c. Selection and Exclusion of Subjects & Randomization procedures

There are two levels of randomization in this study. First, participants were randomly approached on the sidewalk. Social groups arriving at the club together were randomly approached using the portal recruitment methodology (Johnson et al., 2012; Miller et al., 2009, 2013b). The first person to cross an imaginary line on the sidewalk in front of the club was approached to recruit this person and their social group. Nightclubs with at least 200 patrons on a typical weekend night were contacted to seek permission to establish a data collection site outside the club. Clubs held different types of events on different nights, attracting different patrons, depending upon the event being featured. A total of 41 events across 7 nightclubs in the San Francisco area were selected for the data collection from June 2016 through October 2017. These events occurred on Friday and Saturday evenings when the attendance was the greatest. Patrons who were attending the club that evening and were arriving with at least one other person who agreed to participate were considered eligible. Anyone working that evening at the club was not eligible. A total of 352 groups, representing 959 patrons were included in the study. The study was able to recruit 25% of the groups that were stopped and given a description of the study and data collection procedures which included breath tests for estimates of blood alcohol levels and oral fluid samples for detecting drug use and surveys at entrance and exit. Retention for the sample was 88% at exit. Recruitment and data collection occurred outdoors with a data collection site adjacent to the entrance to the club. Participants provided informed consent, and all study procedures were approved by the Pacific Institute for Research Evaluation's Institutional Review Board.

d. Survey and Randomization Procedures

Once patrons agreed to participate in the study, each participant was given a unique number on a wrist band that allowed matching of individuals within a group and entrance/exit data. No names were collected to provide anonymity.

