Legally intoxicated: Breathalyzer readings were recorded and all participants who were at a reading of .08 % alcohol or higher, were considered to be legally intoxicated.

Prevalence of recreational drug use: Oral fluid samples were sent to an outside laboratory for analyses. Substances were assayed into the following seven categories (1) tetrahydrocannabinol (THC); (2) cocaine-including benzoylecgonine, cocaethylene, norcocaine; (3) amphetamine/3,4-methylenedioxy-methamphetamine(MDMA), including methamphetamine, methylenedioxyamphetamine (MDA), and methylenedioxyethylamphetamine(MDEA); (4) opiates/analgesics, including morphine, codeine, oxymorphone,6 a.m., hydrocodone, hydromorphone, and oxycodone; (5). methadone; (6). phencyclidine (PCP); and (7). ketamine. Any drug use was considered positive for drug use.

Leaving club with Friends arrived with: At exit, participants were asked if they were leaving the club with the same group of friends with whom they arrived.

Other Pre-Specified outcomes

Experienced sexual aggression: While at the club, the respondent was asked if someone touching them sexually in a way that they did not want to be touched or did something else sexual to the respondent that they did not want them to do

Experienced physical aggression: While at the club, respondent was asked if someone intentionally pushed, shoved, or punched

Experienced sexual harassment: While at the club, respondent was asked if sexually came on to them after indicating no interest

f. Sample characteristics

The average age of participants was 28 years and 43% were female. A fifth of the sample identified as Hispanic or Latino and racial characteristics were as follows: 44% white, 21% Asian, 18% unknown or not reported, 8% Black, 7% more than one race, 2% Native Hawaiian or other Pacific Islander, 1% American Indian or Alaska Native.

g. Analyses

Number of Protective actions to keep the Group Safe: These items were summed to create an index of protective actions for each individual. Then an average score was created within the group based upon the scores of each group member divided by the number of individuals in the group. This provided an overall indicator of how safe the group was because of the collective action of the members. *Protective action reported for physical aggression incident:* Among those who experienced physical aggression, the percent who reported some protective action by a member of their group was reported.

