multiracial, 6.8% other, and 9.5% unknown. Slightly more than a fifth (21.1%) were Hispanic. The average age was 27.99 years (SD=6.35). The average group size was 3.38 persons (SD1.43).

Descriptive analyses were conducted for the overall group and for the experimental and control groups. To account for the clustering within event and group, mixed-model regressions in SPSS were used to test simple effects of the intervention on continuous background variables. Parallel models were conducted for categorical background variables using Mplus Version 7 (Muthen & Muthen, 1998-2015).For key outcomes, multilevel models via mixed-model regressions in SPSS 21 were conducted to account for nesting by event and group. Analyses used an intent-to-treat approach to examine assignment to the intervention as a predictor, controlling for background variables, history of drinking/other drug use and risk level. Listwise deletion was used for missing cases.

IV. Assessment of Efficacy-Overview

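### Unrestricted listwise deletion in covariate-adjusted models drops patrons with a measured exit outcome when a baseline covariate is blank, losing precision needlessly

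*Combined protocol and SAP*

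**What the plan says.** Section III.g (Analyses) states that, for the key outcomes, "multilevel models via mixed-model regressions in SPSS 21 were conducted to account for nesting by event and group". On the principle behind these models it says: "Analyses used an intent-to-treat approach to examine assignment to the intervention as a predictor". The adjustment set is given only in general terms, as "controlling for background variables, history of drinking/other drug use and risk level". The individual covariates are not listed. The next sentence is the only missing-data rule: "Listwise deletion was used for missing cases". It does not separate a missing exit outcome from a missing baseline covariate. The document gives no imputation, missing-indicator method, sensitivity analysis or number analysed per model.

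On the sample, Section III.c states "A total of 352 groups, representing 959 patrons were included in the study" and "Retention for the sample was 88% at exit". Section III.d places assignment after baseline collection was complete for the whole group.

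On completeness of the background variables, the document offers only the race tables. The one in III.g ends with "multiracial, 6.8% other, and 9.5% unknown", and the one in III.f has "18% unknown or not reported".

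**The concern.** A regression that deletes listwise needs the outcome and every covariate to be present. A patron who came back out, gave a breath and oral fluid sample and completed the exit survey is therefore discarded if one adjustment variable is blank. This is separate from the roughly 12% with no exit data, whose outcomes cannot be recovered by any handling of covariates.

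Covariate adjustment is meant to sharpen the comparison, and deleting measured outcomes gives part of that gain back. An analysis described as intent-to-treat also then omits people who were assigned and whose outcome is known. The estimate refers to patrons with complete baseline answers, not to everyone measured. Because the blanks arose before assignment, they cannot be caused by the arm, so the arm comparison itself is not expected to be biased. For the same reason the deletion is avoidable: in a randomised comparison, simple fills made without regard to arm are valid for baseline covariates.

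**Working it through.** The plan has no figure to reproduce. It gives no sample-size calculation, within-group correlation, count of blank covariates or number analysed. The check below is an illustration.

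**Inputs from the documents:** 959 patrons, 352 groups, 88% retained at exit (all III.c).

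**Assumed inputs:** the share *p* of exit-measured patrons with at least one blank covariate, and the within-group correlation ρ. The value *p* = 9.5% borrows the unknown-race share in III.g as a round scenario. Many small gaps would reach the same level: ten covariates, each independently 1% blank, give 1 − 0.99¹⁰ = 9.6%.

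**1. Patrons measured at exit.** 0.88 × 959 = 844 (839 to 849, allowing for rounding of 88%).

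**2. Patrons kept under listwise deletion.** 844 × (1 − 0.095) = 764, so about 80 are lost.

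**3. Standard error if patrons were independent.** √(844/764) = 1.051, a rise of about 5%.

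**4. Standard error with clustering.** Effective size = n / [1 + (m − 1)ρ], where m is the mean number analysed per group: 844/352 = 2.40 before and 764/352 = 2.17 after.

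| ρ | Effective size before | Effective size after | SE ratio |
|---|---|---|---|
| 0.2 | 844/1.280 = 659.6 | 764/1.234 = 619.1 | √(659.6/619.1) = 1.032 |
| 0.5 | 844/1.699 = 496.8 | 764/1.585 = 481.9 | √(496.8/481.9) = 1.015 |

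**5. Power.** For an effect that would have 80% power (two-sided 5%, assumed), power is Φ[(1.960 + 0.842)/SE ratio − 1.960]. That gives 76.0% with independent patrons and 78.8% at ρ = 0.5.

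**6. A smaller gap.** At *p* = 5%, 42 patrons are lost and 802 remain. The standard error rises 2.6% with independent patrons and 0.8% at ρ = 0.5. At *p* = 0 nothing is lost.

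**7. The first primary outcome.** III.g averages individual scores within the group. If every member carries that group score, ρ = 1 and the effective size is n/m = 352 before and after, a ratio of 1.00. Information goes only when a group loses all its analysed members.

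**8. What filling recovers.** This was simulated with 1,000 runs per setting, 352 groups, a true effect of 0.20, one covariate correlated 0.5 with a continuous outcome, ρ = 0.1, 12% random exit loss and cluster-robust standard errors. At *p* = 9.5% the mean standard error was 0.0642 with complete covariates, 0.0670 with listwise deletion, and 0.0651 with a mean fill plus missing indicator. The fill recovers (0.0670 − 0.0651)/(0.0670 − 0.0642) = 68% of the lost precision. Both methods gave mean estimates of about 0.20. They also did so in a run at ρ = 0.3 where missingness depended on the covariate's own value.

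**The case against.** The strongest reply is that nothing in the documents shows a patron was actually lost this way. Much of it stands.

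- **Race.** The documents never say race was a covariate. The shares in III.g sum to 44.2 + 21.5 + 7.9 + 1.7 + 1.3 + 7.1 + 6.8 + 9.5 = 100.0%, with unknown tabulated as a level. If the model coded it the same way, the loss from race is zero.
- **The 18% figure.** A reader might infer from III.f that 18% of patrons, about 152 of 844, were dropped. The documents do not support this. III.f has no category for other, while III.g has 6.8% other and 9.5% unknown, together 16.3%. The remaining shares agree to within a point, so the 18% probably includes patrons who did answer.
- **Sex and history items.** A reader might also take the two shares of women (43% in III.f, 45.3% in III.g) as a sign of missing sex entries. A different analysis sample or further gender categories would fit as well. No figure in the documents shows non-response on drinking or drug history.
- **Primary outcomes.** The group-averaged first primary outcome would be little affected if averaging came before deletion, but the order is not stated. III.g describes the two aggression-related primary outcomes only as percentages among those with an incident.
- **Exit loss.** The roughly 115 patrons without exit data (959 − 844) are the larger threat to the intent-to-treat label, and filling covariates does nothing for them.

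These points limit the size. They do not change the written rule, which as it stands deletes measured outcomes. Nor do they remove the availability of a better method at little cost.

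**Conclusion.** The point holds as a statement about the rule. Unrestricted listwise deletion in an adjusted model removes patrons with a measured exit outcome for a blank covariate. That loses precision needlessly and falls short of the intent-to-treat label. It is not a claim of bias: baseline preceded assignment, and none is expected in the arm comparison.

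The size cannot be derived and may be zero. The 9.5% scenario is an illustration that rests on the assumed share, equal-sized groups and the assumed correlation. Because patrons were recruited and assigned in groups, the 1.5% to 3% rise is the more relevant range, and the 5% for independent patrons is an outer figure. The effect falls mainly on patron-level outcomes such as legal intoxication, drug use and leaving with the same friends.

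**What to change.** The trial is complete and results are summarised in Section IV. The existing sentence should therefore stay as the description of those results, with a labelled addition to III.g along these lines:

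*In an added analysis, specified after the main results were known and reported alongside them, listwise deletion was limited to patrons without the exit outcome. Missing baseline covariates were filled without regard to arm, using an unknown category for categorical variables and the overall mean plus a missing indicator for continuous ones. For each model and arm we report the number analysed and the number dropped in the original analysis for a missing covariate alone.*

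This keeps a stated rule for the roughly 12% without exit data, which simply replacing the sentence would remove. The addition should also say whether individual scores were averaged within groups before or after deletion. If the count dropped for covariates alone is zero, one sentence saying so closes the point and no rerun is needed.

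The cost is a short addition to III.g and a rerun of existing models. There are three downsides. The models gain a few extra terms. Only most of the lost precision returns (68% in the setting shown). In any model fitted as logistic, the adjusted effect may shift slightly.

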Computer tablets were handed to each participant to complete the entrance survey. Oral fluid samples for drug analyses and breath tests for determining blood alcohol level were collected during this time by trained research staff. Groups were randomly assigned to either experimental or control after the data for the entire group was collected at baseline. At this point, the research assistant was made aware of the random assignment to either experimental or control condition for the group. Randomization was determined by a randoms number table that determine whether the first group was experimental or control. Given that multiple groups were recruited simultaneously, the supervisor was tracking the assignments of condition and alerting the research assistants as to this assignment. The experimental condition consisted of the Nightlife Safety Plans (NSP) intervention described above. The control condition was given the Fire safety information described above. Given that both the experimental and control group conditions focused on safety in the club, we did not disclose to the participants which safety intervention was under investigation in this study. Once the group finished, they were given an incentive (\$15) and reminded that we would complete a survey when they exited the club with an additional incentive (\$25) offered. As patrons exited the club, they were surveyed again, using the same procedures established at entrance.

e. Measures

Primary Outcomes:

Number of Protective actions to keep the Group Safe: For each individual, five types of actions were assessed related to identifying a potential problem (observing overuse, physical, or sexual aggression) for a friend: There were 5 possible actions to keep their group members safe that were assessed at exit from club (checked in with friends to assess safety during evening, monitored group members alcohol consumption, encouraged pacing drinking, discouraged drug use, encouraged steps to sober up).

Protective action reported for physical aggression incident: Among those who experienced physical aggression, the prevalence of a group member taking action(s) to intervene was reported.

Protective action reported for sexual aggression incident: Among those who experienced sexual aggression, the prevalence of a group member taking action(s) to intervene was reported.

Secondary outcomes

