Protective action reported for sexual aggression incident: Among those who experienced sexual aggression, the percent who reported some protective action by a member of their group was reported.

Legally intoxicated: Percent who were legally intoxicated (BAC.08% or higher). Breath samples provided an estimate of the blood alcohol concentration (BAC) and the MarkV Alcovisor (PAS Systems International, Fredericksburg VA) was used to obtain the breath samples. The estimate of the BAC is presented as measured by this device. Given the short window of time (average of 1 hour 54 minutes, SD=1 hour, 3 minutes) that persons were in the club, only exit BAC is used to reflect drinking and this represents a cumulative total for the evening. Level of intoxication reported which reflects the legal standard of BAC= 0.08% or higher.

Prevalence of recreational drug use: Any use of recreational drugs present in oral fluid tests based upon lab results. Laboratory analyses were conducted using the Quantisal collection device (Immunalysis Corporation, Pomona, CA) to assess the following drug categories: (a)Tetrahydrocannabinol (THC); (b) cocaine, including benzoylecogonine, coaethylene, and norcocaine; (c) amphetamine/e, 4 methylenedioxy-methamphetamine (MDMA), methamphetamine, methylenedioxy-amphetiamen (MDA), and methylenedioxyethylamphetamine (MDEA); (d) opiates/analgesics, including morphine, codeine, oxymorphone, 6-acetylmorphine, hydrocodone, hydropmophone, and oxycodone; (3) methadone; (f) phycyclidine (PCP), and (g) ketamine. Self-report of GHB was also assessed (no lab tests were available for this drug). The prevalence of any drug use at exit from the club was created.

Physical Aggression experienced: Participants were asked at the exit survey whether anyone had intentionally pushed, shoved, or punched you while at the club during the evening.

Sexual aggression experienced: Participants were asked at the exit survey whether anyone had touched you in a sexual way that you did not want or do something else sexual to you that you didn't want them to do.

Leaving club with friends arrived with: The prevalence of the safety action to leave the club with the same friends with whom they arrived.

Females comprised 45.3% of the sample. Ethnicity/race was as follows: 44.2% White, 21.5% Asian, 7.9% African American, 1.7% Pacific Islander, 1.3% Native American, 7.1%

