Exposure to the intervention, NSP, significantly increased the number of safety actions taken within the group to protect others in their group from the unintended consequences from behaviors and experiences in the club that evening related to alcohol use and drug use (Byrnes, Miller, et al., 2019a). The study found that group cohesion related to fewer safety strategies being used and that group cohesion was unrelated to AOD use (Byrnes, Miller, et al., 2019b). This suggests that more risk taking behavior may occur when groups are familiar and comfortable with each other, possibly lowering their sense of risks. The relatively low rates of experiencing physical and sexual aggression impacted the power of the intervention to assess protective actions related to physical or sexual incidents that occurred in the evening. Although the main focus of the intervention was on taking actions to reduce harms, there was also an impact on a secondary outcome related to alcohol use. For participants exposed to NSP, there was a significantly lower BAC at exit. Prevalence of recreational drug use was not impacted by the intervention but prior research (Miller et al., 2013b) indicates that few club patrons (<6%) convert from no drug use at entry to drug use at exit, indicating that recreational drug use has already been initiated prior to coming to the club. The intervention did not significantly alter the rates of physical or sexual aggression while at the club. However, aggression experiences are less under the control of the participants as persons outside the group can be the offender in these incidents. Thus, the group can respond and de-escalate the impact of the aggression but may not be effective at keeping aggressive incidents from happening. Finally, participants exposed to the intervention were significantly more likely to leave as a group and "stick together." Given that the intervention was focused on promoting looking after each other for the evening,

this was an important safety impact. There are anecdotal reports of individuals leaving the club with someone they just met or being assaulted while traveling home by themselves. However, data on the prevalence of this type of experience is not available from prior studies or this study.

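### Section IV reads a comparison of exit drug use as showing no impact, although on the document's own conversion figure it was probably underpowered even for a fully effective intervention unless few patrons were positive at entry

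*Combined protocol and SAP*

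**What the plan says.** Section III.e (Measures) lists recreational drug use as a secondary outcome. Section III.g (Analyses) defines it by status at the end of the visit: "The prevalence of any drug use at exit from the club was created". New use since entry is not defined as an outcome.

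An entry measurement exists. In Section III.d, on the entrance procedures, "Oral fluid samples for drug analyses and breath tests for determining blood alcohol level were collected during this time by trained research staff", and groups were assigned only after the whole group's baseline data had been collected. The key-outcome models in Section III.g are described as "controlling for background variables, history of drinking/other drug use and risk level". The entry oral-fluid result is not named among the covariates.

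Section IV concludes that "Prevalence of recreational drug use was not impacted by the intervention". It goes on to cite earlier work on how rarely patrons change status between entry and exit (under 6%), and takes this low rate as "indicating that recreational drug use has already been initiated prior to coming to the club". No arm difference, confidence interval, test result or power figure is given for this outcome.

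**The concern.** Two statements in one sentence of Section IV pull against each other. If most drug use found at exit began before the group reached the club, exit prevalence is largely fixed before assignment, and the intervention can act only on the small remainder. A non-significant comparison of such an outcome says little about whether that remainder changed. The sentence nevertheless words the result as absence of effect and uses the low conversion rate to explain it, not to limit what it can show.

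Section IV is more careful elsewhere. It says the rates of aggression were not significantly altered, and that low incident rates reduced power for the protective-action outcomes. At stake is how a named secondary outcome is read: as evidence that the intervention does nothing for drug use within the evening, or as a comparison with limited ability to tell.

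**Working it through.** The document gives no sample-size, power or detectable-difference figure, so there is none to reproduce.

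**Inputs from the document**
- Sample (Section III.c): "A total of 352 groups, representing 959 patrons were included in the study", so 959/352 = 2.72 per group.
- Retention (Section III.c): "Retention for the sample was 88% at exit", so 0.88 × 959 = 844 patrons at exit and 0.88 × 2.72 = 2.40 per group. Listwise deletion (Section III.g) could lower the analysed number further.
- Conversion between entry and exit: under 6%, from prior research. Its denominator is not stated, so both readings are run.

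**Assumptions (not in the document)**
- 1:1 allocation, so 844/2 = 422 per arm; two-sided alpha 0.05.
- Entry prevalence e of 10% to 50%.
- Within-group correlation (ICC) of 0 or 0.3; event-level clustering is not modelled.
- Fully effective means no conversions in the intervention arm, with entry-positive patrons still positive at exit.

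**Largest possible effect.** If 6% is a share of all patrons, d = 6 points. If it is a share of entry-negative patrons, d = 6% × (1 − e); at e = 30% this is 0.06 × 0.70 = 4.2 points.

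**Power without adjustment for entry status.** Design effect DE = 1 + (2.40 − 1) × ICC, which is 1.00 or 1.42. Effective n per arm = 422/DE, which is 422 or 297. Control prevalence p1 = e + d, intervention prevalence p2 = e, and p̄ is their mean.

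Power = Φ[(d − 1.96·SE0)/SE1], where SE0 = √(2p̄(1 − p̄)/n) and SE1 = √((p1(1 − p1) + p2(1 − p2))/n).

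Example with e = 30%, d = 6 points, ICC 0: SE0 = 0.0324 and SE1 = 0.0323, so (0.06 − 1.96 × 0.0324)/0.0323 ≈ −0.11 and power is 46%. With ICC 0.3: SE0 = 0.0386 and SE1 = 0.0385, giving −0.40 and power of 34%.

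| Entry prevalence | 6% of all, ICC 0 | 6% of all, ICC 0.3 | 6% of negatives, ICC 0 | 6% of negatives, ICC 0.3 |
|---|---|---|---|---|
| 10% | 74% | 59% | 65% | 51% |
| 20% | 54% | 41% | 39% | 29% |
| 30% | 46% | 34% | 26% | 19% |
| 40% | 42% | 32% | 18% | 14% |
| 50% | 42% | 31% | 14% | 11% |

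**Detectable difference at 80% power.** 6.6 to 9.6 points with ICC 0 and 8.0 to 11.5 points with ICC 0.3, against a ceiling of 6.

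**Where power reaches 80%.** Only if entry prevalence is below 7.9% (of all) or 6.6% (of negatives) with ICC 0, and below 4.4% or 3.9% with ICC 0.3.

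**Sensitivity.**
- If conversion is 3%, power over the same grid is 5.5% to 27.6%.
- With the stated average group size of 3.38 in place of 2.40, power at e = 30%, ICC 0.3 and 6% of all patrons falls from 34% to 29%.

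**What entry status would add.**
- New use among entry-negative patrons, 6% against 0%, has 95% to 99.8% power with ICC 0 and 86% to 98% with ICC 0.3, for e of 10% to 50%.
- Simulated power for exit status adjusted for the entry test (4,000 runs; 6% of negatives; e of 10%, 30% and 50%) is at least 99%. This is optimistic: it ignores clustering and lets every entry-positive patron remain positive.

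**The case against.** Much of the other side stands.

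- A reader might infer that the comparison could not detect any effect, or that drug use could not be assessed in this trial. The document supports neither. Power in the best case is low to moderate, up to 74% at 10% entry prevalence and above 80% at very low prevalence. Entry samples were collected, so a sharper analysis was possible.
- The conversion figure alone does not settle power. Prevalence, ICC, allocation ratio and alpha are also needed, and none is given. The figure comes from earlier research, and Section III.g also counts self-reported GHB, which that figure may or may not cover.
- The calculation is for a crude comparison. The planned models adjust for history of use and risk level, which should predict exit status. The gain needed varies: 80% power for 6 points requires SE = 0.06/2.8 = 0.0214. With ICC 0 the covariates would have to explain 1 − (0.0214/0.0231)² ≈ 14% of the variance at e = 10%, but 1 − (0.0214/0.0323)² ≈ 56% at e = 30%. Whether they did is unknown.
- The sentence carries part of its own caveat, since it tells the reader that little conversion was to be expected.
- Section IV is an overview and gives no estimates for any outcome. The cited outcome paper may report them, or an entry-adjusted analysis.

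These points narrow the claim but do not support the flat wording. The caveat explains why a null result might be expected; it does not say that the comparison was weak.

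**Conclusion.** The concern holds in a limited form. On the document's own conversion figure, the intervention could lower exit prevalence by at most about 6 points. A comparison not adjusted for entry drug status was probably underpowered even for that: about 11% to 74% power for entry prevalence of 10% to 50% and ICC 0 to 0.3, reaching 80% only below about 4% to 8%. Because the figure is an upper bound and complete prevention is the best case, power for a smaller effect would be lower.

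This rests on 422 patrons per arm, two-sided 0.05, the prior-research figure applying here, entry-positive patrons remaining positive at exit, and no gain from the planned covariates. It also reads the Section IV statement as reporting a non-significant test, since no result is shown. It does not show that the intervention affected drug use, or that the question was unanswerable. The point concerns the wording of one secondary outcome and a baseline measurement not named in its model.

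**What to change.** 1. Keep any drug use at exit as the named secondary outcome, and add the entry oral-fluid result as a covariate in its model. If it was already included, say so in Section III.g.
2. Report the arm difference in exit prevalence with its 95% CI, with the entry prevalence and the number analysed per arm.
3. In Section IV, replace the statement of no impact with *no significant difference was detected* (if the refitted model bears this out), and note the limited ability to detect change within the evening.
4. Optionally, report new use among entry-negative participants as a clearly labelled post hoc sensitivity analysis. It should not replace the named outcome, because it would be chosen after a null result was known.

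Cost: one refitted model on data already collected, a reworded sentence, and the loss of participants without an entry result. The added adjustment must also be labelled as chosen after results were known.
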